6.1 Antibiotic resistance rate

Minimal inhibitory concentrations (MIC) of clarithromycin $>2 \mu\text{g/mL}$, metronidazole $>8 \mu\text{g/mL}$, levofloxacin $>2 \mu\text{g/mL}$ is defined as resistance breakpoints. Antibiotic resistance rate is defined as the number of patients with antibiotic resistant strains divided by the total number of population for analysis. These data are presented with number, percentage.

6.2 Effect of antibiotic resistance on eradication rate

Comparisons of eradication rate of one therapy between antibiotic susceptible and

resistant strains will be performed in the PP analysis populations using the Pearson's χ^2 , corrected χ^2 or Fisher's exact test.

Additional comparisons of eradication rate of antibiotic resistant strains between the tailored therapy and the empiric therapy will be performed in the PP analysis populations using the Pearson's χ^2 , corrected χ^2 or Fisher's exact test.

6.3 Effect of presence of adverse events on compliance.

Comparisons of compliance rate of one therapy between presence and absence of adverse event will be performed in the safety analysis populations using the Pearson's χ^2 , corrected χ^2 or Fisher's exact test.

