10.3 Statistical methods

Comparative superiority of the two groups was assessed through hypothesis testing (one-sided Z test) and derivation of a two-sided 95% confidence interval (CI) of difference based on H. pylori eradication rate. If p-value of the testing less than 0.025 and the lower bound of the 95% CI greater than zero, superiority of susceptibility-based therapy over empirical therapy could be concluded.

Between-group differences were evaluated using Student's t-test for continuous variables and Pearson's χ^2 /corrected χ^2 or Fisher's exact test for categorical variables, as appropriate. All p-values were two-sided except the testing of superiority, and were considered statistically significant if p-value less than 0.05.

Subgroup analyses of eradication efficacy were performed based on the results of antibiotic susceptibility test and compliance assessment.

11 Ethical principles

The study is registered in ClinicalTrials.gov. The study protocol is approved by the Ethics Committee at all institutions, and the study will be performed according to good clinical practice and the Declaration of Helsinki.

Before each patient is selected into the study, the physician of the study have the responsibility to tell patients or their designated agents the purpose, process, completion and comprehensively introduce possible adverse reactions, risks to bear, possible benefits and other information all-round and detailed, making the patients know their rights. We are ordered to inform the patients of having the right to decide whether to participate in the study, as well as the right to withdraw the study at any time without any discrimination. The patients or their legal representatives should sign the informed consent after carefully reading and fully understanding, and retain the signature page of the copy.

12 References

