Subjects without AEs

Subjects with AEs

Total

AE, adverse event.

Final Statistical Analysis Plan

This statistical analysis plan includes the details of study sample size calculation and statistical methods for analysis of outcomes and safety.

Table of Contents

1. Sample size estimation	68
2. Definition of populations for analysis	68
3. Evaluation of baseline characteristics	68
4. Evaluation of primary outcomes	70
5. Evaluation of secondary outcomes	70
6. Additional analyses	72
7. Table Design	73

1. Sample size estimation

Assuming 96.5% eradication rate of susceptibility-based therapy in our trial, 88.9% eradication rate of empirical therapy, a superiority margin of >0 , a power of 80%, an alpha of 0.05 (one-sided), a ratio of 3:1, at least 260 subjects in susceptibility-based therapy and 87 subjects in empirical therapy will be required to show superiority of susceptibility-based therapy over empirical therapy on the basis of H. pylori eradication rate. Taking into consideration of 10% lost to follow-up, at least 382 participants (286 for tailored therapy and 96 for empiric therapy) is expected to be recruited for the study.

2. Definition of populations for analysis

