6.4 Effect of compliance on eradication rate

Comparisons of eradication rate of one therapy between good and poor compliance will be performed in the ITT analysis populations who had UBT results using the Pearson's χ^2 , corrected χ^2 or Fisher's exact test.

7. Table Design

Table 1. Baseline characteristics

Variables	Tailored therapy	Empiric therapy	p value
Age, years (range)			
Gender (male/female)			
Diagnosis (Dyspepsia/PUD)			
Antibiotic resistance pattern			
Clarithromycin, n (%)			
Metronidazole, n (%)			
Levofloxacin, n (%)			
All-susceptible, n (%)			
Triple-resistant, n (%)			
Poor adherence*			
Loss of follow-up			

Final SAP

NUD, non-ulcer dyspepsia; PUD, healed peptic ulcer disease.

* Poor adherence, took less than 80% of drugs

Table 2. Eradication rate of each group in ITT and PP analysis

Analysis	Tailored therapy	Empiric therapy	Difference	p value for inequality*	p value for superiority **
ITT (% , n/N)					
95% CI					
PP (% , n/N)					
95% CI					

CI= confidence interval; ITT = intention-to-treat; PP = per-protocol.

* The *p* values were for testing the difference between tailored therapy group and empiric therapy group.

** The *p* values were for testing the superiority of tailored therapy group to empiric therapy group.

Table 3. antibiotic resistance pattern of ITT population

antibiotic resistance pattern (CLA-MET-LEV)	ITT population	Tailored therapy	Empiric therapy
All susceptible			
S-S-S			
Single resistant			
R-S-S			
S-R-S			
S-S-R			
Dual resistant			
R-R-S			
R-S-R			
S-R-R			
Triple resistant			
R-R-R			

CLA, clarithromycin; LEV, levofloxacin; MET, metronidazole; R, resistant; S, susceptible.

Table 4. Eradication rates of tailored and empiric therapy in the presence of antibiotic resistance in the per-protocol population

PP population	Tailored therapy	Empiric therapy	p value
Clarithromycin resistance			
Susceptible			
Resistant			
Metronidazole resistance			
Susceptible			
Resistant			
Levofloxacin resistance			
Susceptible			
Resistant			
Resistance pattern (Clarithromycin-Metronidazole-Levofloxacin)			
S-X-X			
R-S-X			
R-R-S			
R-R-R			

R=resistant; S=susceptible; X=resistant or susceptible.

Table 5. Adverse events and adherence in the treatment groups

Variables	Tailored therapy	Empiric therapy	p value*
Total, n/N (%)			
AE grade			
None/Mild/Moderate/Severe			
AE variety			
Taste alteration			
Dyspepsia			
.....			
.....			
.....			

Skin rash

Discontinued drugs

because of AEs

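### Final SAP Table 4 tests tailored against empiric therapy row by row in ten resistance rows, with no interaction test and no interval for the row differences, so a uniform benefit would usually look strain-specific

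*Combined protocol and SAP*

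**What the plan says.** Final Protocol 10.3 announces the subgroup work in one sentence: "Subgroup analyses of eradication efficacy were performed based on the results of antibiotic susceptibility test and compliance assessment". The same section sets the threshold: "All p-values were two-sided except the testing of superiority, and were considered statistically significant if p-value less than 0.05".

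Final SAP 6.2, under Additional analyses, has two parts, both in the per-protocol population and both by Pearson, corrected chi-square or Fisher test. The first compares susceptible with resistant strains inside one therapy. The second is "Additional comparisons of eradication rate of antibiotic resistant strains between the tailored therapy and the empiric therapy".

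Table 4 in Final SAP section 7 is wider than that text. It has columns for tailored, empiric and p value. Its rows are susceptible and resistant for clarithromycin, metronidazole and levofloxacin, followed by a block headed "Resistance pattern (Clarithromycin-Metronidazole-Levofloxacin)" with S-X-X, R-S-X, R-R-S and R-R-R. The p value column therefore covers susceptible rows too. The table key defines X as either state, which makes S-X-X the same patients as the clarithromycin-susceptible row.

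Neither final document mentions an interaction or heterogeneity test, a confidence interval for a row difference, a multiplicity rule, or any limit on how the rows may be interpreted. No rule is given for choosing among the three tests.

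**The concern.** A reader of Table 4 will naturally ask whether tailoring helps more in some strains than in others. The tailored regimen changes with exactly the four listed patterns, so the question is a fair one. The table answers a different question: whether each row, taken alone, reaches p<0.05. With one true effect throughout, that depends mainly on row size, and the rows differ about tenfold in size.

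At stake is the interpretation of a secondary objective. A column with some p values below 0.05 and others above invites the statement that tailored therapy works in the first group of strains and not in the second, when no planned analysis compares the groups.

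**Working it through.** **Reproducing the plan's figure.** Final SAP section 1 has "Assuming 96.5% eradication rate of susceptibility-based therapy in our trial, 88.9% eradication rate of empirical therapy", "an alpha of 0.05 (one-sided), a ratio of 3:1" and 80% power. With pooled variance, p̄ = (0.889 + 3×0.965)/4 = 0.946 and

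n(empiric) = [1.645√(0.946×0.054×4/3) + 0.842√(0.889×0.111 + 0.965×0.035/3)]² / 0.076² = (0.429 + 0.279)²/0.005776 ≈ 86.9.

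This rounds to 87, and 3×87 = 261, against the stated "at least 260 subjects in susceptibility-based therapy and 87 subjects in empirical therapy will be required". The figure reproduces to within one patient.

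**Row sizes.** The SAP says "at least 382 participants (286 for tailored therapy and 96 for empiric therapy) is expected to be recruited". After the planned 10% loss, 0.9×286 ≈ 257 and 0.9×96 ≈ 86 are analysed. The Final Protocol Background cites resistance of 21–52% (clarithromycin), 61–95% (metronidazole), 20–54% (levofloxacin) and 21–37% (clarithromycin plus metronidazole). The midpoints are 36.5%, 78%, 37% and 29%. Levofloxacin resistance is assumed independent of the other two.

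**Power per row for the uniform 7.6-point difference**, two-sided 0.05, normal approximation: Φ[(0.076√n − 1.960×0.261)/0.332], where n is the number of empiric patients in the row.

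| Row | Share | Empiric n of 86 | Approx. power |
|---|---|---|---|
| Clarithromycin S (= S-X-X) | 63.5% | 55 | 56% |
| Clarithromycin R | 36.5% | 31 | 40% |
| Metronidazole S | 22% | 19 | 29% |
| Metronidazole R | 78% | 67 | 63% |
| Levofloxacin S | 63% | 54 | 56% |
| Levofloxacin R | 37% | 32 | 40% |
| R-S-X | 36.5 − 29 = 7.5% | 6 | 16% |
| R-R-S | 29×0.63 = 18.3% | 16 | 27% |
| R-R-R | 29×0.37 = 10.7% | 9 | 20% |

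The approximation is generous in small rows. In simulation, R-S-X has about 4–5% power and metronidazole-resistant 54% when the test is chosen by expected counts. With Pearson throughout the figures are 14% and 64%.

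**Hand check of a split pair.** The two rows for one drug hold different patients, so the chance that exactly one is significant is P₁(1−P₂) + P₂(1−P₁). For metronidazole this is 0.63×0.71 + 0.29×0.37 ≈ 0.55. For clarithromycin it is 0.56×0.60 + 0.40×0.44 ≈ 0.51. Each drug alone splits in about half of trials.

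**Simulation of Table 4 at 257/86.** Two test rules were run because the SAP names none. (a) uses Pearson if the smallest expected count is at least 5, corrected chi-square if it is 1–5 with at least 40 patients in the row, and Fisher otherwise. (b) uses Pearson only.

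| Event | (a) | (b) |
|---|---|---|
| Uniform 96.5% v 88.9%: at least one drug split | 72% | 80% |
| Uniform 96.5% v 88.9%: four patterns mixed | 56% | 76% |
| No benefit, 93% v 93%: at least one significant row | 10–11% | 25–26% |

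Across several prevalence settings drawn from the cited ranges, at 260/87 and 286/96, a split drug appears in 71–79% of trials under (a) and 76–85% under (b). All ten rows are significant in fewer than 1%.

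**What an interaction test would do.** A penalised-likelihood (Firth) logistic test over the four patterns, under the same uniform rates, rejects in about 1% of trials. That is below the nominal 5% because failures are few and R-S-X has only six or seven controls. If the benefit is absent in R-R-R only, it rejects in about 3%. If a 12-point benefit exists only in S-X-X, it rejects in about 35%, a figure that moves with the rates assumed.

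**The case against.** Several points on the other side stand.

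- These are additional analyses. The superiority test in Final SAP 4.3 is untouched, and nothing in the plan licenses a subgroup claim from Table 4.
- Secondary objective (2) concerns the effect of resistance on eradication, and the first part of 6.2 addresses that directly within each therapy. A reader might infer that the objective is left without any analysis; the text does not support that.
- A reader might also infer that the table would mislead clinicians about whom to test before treatment. It cannot do so: resistance status is the result of that test and is unknown beforehand.
- The 6.2 text names between-arm tests for resistant strains only. The susceptible-row tests come from the table's p value column, and the 0.05 threshold comes from the protocol.
- A uniform benefit is a stylised case. Tailored patients receive different regimens by pattern, and R-R-R patients receive a bismuth, amoxicillin and metronidazole quadruple regimen, as controls do. Unequal effects are plausible.
- It is tempting to present an interaction test as the cure, with false claims held at 5%. The test is much more conservative than that and would miss most real differences.

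None of this removes the defect. Row p values are not a more powerful test of heterogeneity; they do not test it at all. Plausible unequal effects make a direct comparison more necessary. The mismatch between text and table needs correcting in any case.

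**Conclusion.** The point holds for a secondary analysis and should be corrected before the data are analysed. In the uniform-benefit case a misleading split for at least one drug is the usual result, at about 72–80% of trials depending on the test rule, and stays at 71–85% across the resistance ranges tried. With no benefit anywhere, an isolated significant row appears in about one trial in ten, or one in four with Pearson only.

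These figures assume equal rates in every strain, levofloxacin resistance independent of the other two, and no per-protocol loss beyond the planned 10%. The harm is a mistaken claim that benefit is confined to certain strains. The documents do not support extending it to the primary result or to the choice of patients for testing.

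**What to change.** In Final SAP Table 4:

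- Replace the p value column by the tailored-minus-empiric difference with a small-sample 95% CI, such as a score interval.
- Delete the clarithromycin-susceptible row or S-X-X, so that no comparison is printed twice.

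In Final SAP 6.2:

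- Align the text with the table by stating which rows, susceptible as well as resistant, are compared between arms.
- Add one pre-specified treatment-by-pattern interaction test over S-X-X, R-S-X, R-R-S and R-R-R. Name its method and scale. A penalised-likelihood logistic model copes with cells that have no failures, but it works on odds ratios while the table shows differences, and the text should say so.
- State that a difference in significance between rows is not evidence of different effects, that a strain-specific claim needs support from the interaction test, and that a non-significant interaction is not evidence of equal effects.

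The cost is SAP and table-shell wording, with no new data. The sponsor gives up row-level significance claims. The interaction test will seldom reject, so the intervals carry most of the information and the test cannot be the main safeguard.

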2.2 The secondary objective

- (1) To compare the safety and compliance of tailored therapy with empiric modified bismuth quadruple therapy;
- (2) To evaluate the impact of antibiotic resistance on eradication rates;
- (3) To evaluate the cost-effectiveness of susceptibility-based tailored therapy in treating naïve patients with *H. pylori* infection.

3. Follow Diagram

4. Study Design

This study is a prospective, superiority-designed, multi-center, open-label, randomized controlled trial conducted in five hospitals in Shanghai, China including Renji Hospital, Ruijin Hospital, Zhongshan Hospital, Shanghai general Hospital, and Shanghai Tenth People's Hospital.

5. Study population

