2.1 Intention--to-treat (ITT) Analysis population

According to the Intention-to-treat principle: All randomized patients will be included in the ITT analysis. Patients who did not return for a follow-up 13C-UBT will be recorded as treatment failures.

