2.2 Per-protocol (PP) analysis population

All individuals who violated the study protocol, such as patients not taking at least 80% of treatment drugs, or with unknown post-treatment H. pylori status will be excluded from the PP analysis.

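### The between-arm comparison of eradication within resistance strata is planned in the per-protocol set only, although an ITT version that keeps the randomised contrast is available from data already collected

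*Combined protocol and SAP*

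**What the plan says.** Final SAP 6.2 plans two analyses by resistance, both in the PP set. The first compares susceptible strains with resistant ones within one therapy; for this contrast with "resistant strains will be performed in the PP analysis populations" the SAP names chi-squared or Fisher tests. The second compares the arms: "Additional comparisons of eradication rate of antibiotic resistant strains between the tailored therapy and the empiric therapy will be performed in the PP analysis" populations. The matching shell is "Table 4. Eradication rates of tailored and empiric therapy in the presence of antibiotic resistance in the per-protocol population". It has rows for each antibiotic and for the combined resistance pattern, a p-value column, and no ITT block.

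The two analysis sets are defined in final SAP section 2. PP drops protocol violators, "such as patients not taking at least 80% of treatment drugs, or with unknown post-treatment H. pylori status will be excluded from the PP analysis". The violations are listed by example, so other departures may also lead to exclusion. ITT keeps everyone randomised, and "Patients who did not return for a follow-up 13C-UBT will be recorded as treatment failures".

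Three other places bear on the point:

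- Final protocol 10.3 says only "Subgroup analyses of eradication efficacy were performed based on the results of antibiotic susceptibility test and compliance assessment". It names no analysis set, so the PP restriction comes from the SAP text and the Table 4 shell.
- Final SAP Table 3 uses the ITT population, but it counts resistance patterns and shows no eradication outcome.
- Final protocol 2.2 lists as a secondary objective "To evaluate the impact of antibiotic resistance on eradication rates". Final SAP 6.2 and Table 4 are where it is addressed.

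**The concern.** A comparison of arms within a stratum keeps the protection of randomisation if the stratum is fixed before allocation and everyone randomised in it is counted. The first condition holds here: susceptibility testing is an enrolment step at day -14, allocation is at day 0, and a positive culture is an entry criterion. The PP restriction gives up the second condition.

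The exclusions need not be balanced. The trial is open label. Under final protocol 6.2 most tailored strata receive three drugs against four in the empirical arm, while triple-resistant tailored patients also receive four. Final protocol 5.3 names severe side effects as a reason for not taking medication as prescribed. The SAP itself treats these events as linked to outcome: 6.3 relates adverse events to compliance, and 6.4 relates compliance to eradication. If exclusions differ by arm, or differ by arm in some strata and not in others, a PP-only Table 4 could change both the level and the pattern of the differences that readers will use to judge in which strains tailoring matters.

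**Working it through.** **Which set is used where (final SAP)**

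| Analysis | Set |
|---|---|
| Primary comparison (4.2, 4.3, Table 2) | ITT and PP |
| Resistance patterns by arm (Table 3) | ITT, no eradication outcome |
| Susceptible v resistant within a therapy (6.2) | PP only |
| Arm v arm by resistance (6.2, Table 4) | PP only |
| Compliance and eradication within a therapy (6.4) | ITT patients with a breath test result |

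No section supplies an ITT version of the fourth row. The ingredients exist: resistance pattern by arm in ITT (Table 3) and the ITT outcome rule (2.1).

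**The plan's own figures.** The plan gives no number for the resistance comparison. Its planned overall effect is 96.5% - 88.9% = 7.6 points (final protocol 10.1). The evaluable sample size stated there, 260 + 87, reproduces as 261 + 87 with pooled variance, one-sided alpha 0.05 and 80% power. The only exclusion figure is 10% loss to follow-up overall, not split by arm.

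**How far PP and ITT can part.** For one stratum, let
- p_T, p_E = PP eradication rates in the tailored and empirical arms;
- x_T, x_E = proportions excluded from PP;
- f = proportion of excluded patients whom ITT counts as eradicated (0 if all are failures, 0.5 if half are).

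The ITT rate in an arm is p(1 - x) + f·x. When p_T = p_E = p, the PP difference is 0 and the ITT difference reduces to (p - f)(x_E - x_T).

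All inputs below are assumptions: p = 0.95, and the exclusion rates shown.

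| Excluded, tailored v empirical | All excluded fail (f = 0) | Half fail (f = 0.5) |
|---|---|---|
| 5% v 10% | 0.95 × 0.05 = +4.75 points | 0.45 × 0.05 = +2.25 points |
| 5% v 15% | 0.95 × 0.10 = +9.5 | 0.45 × 0.10 = +4.5 |
| 10% v 10% | 0 | 0 |
| 10% v 5% | -4.75 | -2.25 |
| 15% v 5% | -9.5 | -4.5 |

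As a second illustration, set the PP rates to the planned 96.5% and 88.9%. These are whole-arm figures, used here only for scale, and they give a PP difference of 7.6 points. With all excluded patients counted as failures:
- 5% v 10% excluded: 0.965 × 0.95 - 0.889 × 0.90 = 0.9168 - 0.8001 = 11.7 points;
- 10% v 5% excluded: 0.965 × 0.90 - 0.889 × 0.95 = 0.8685 - 0.8446 = 2.4 points;
- 10% v 10% excluded: 0.8685 - 0.8001 = 6.8 points.

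The gap between PP and ITT therefore depends mainly on the imbalance in exclusions, which the documents do not give.

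**The case against.** The case for leaving the plan alone has real substance.

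- **PP suits part of 6.2.** The secondary objective is answered most directly by comparing susceptible with resistant strains within a therapy. Resistance is not randomised, so that contrast has no randomisation to lose, and counting missing tests as failures would mix loss to follow-up into a question about drug activity. This stands: that comparison may stay in PP. It does not cover the between-arm comparison.
- **These are additional analyses.** The SAP files 6.2 under that heading, and no superiority decision attaches to Table 4. This stands and limits the weight of the point.
- **Tolerability is reported elsewhere.** Table 5 gives adverse events, discontinuations and adherence by arm, and Table 1 gives poor adherence and loss to follow-up. This is a partial answer, because none of it is split by resistance pattern.

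Three stronger readings are tempting, and the documents do not support them:

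- A reader might infer that Table 4 cannot be reconciled with the primary result. It can be set beside the PP row of Table 2.
- A reader might infer that PP hides a benefit of tailoring. Without exclusion rates by arm the sign is unknown, and the table above runs both ways.
- A reader might blame PP for thin strata. At the 61 to 95% metronidazole resistance in the protocol's background, susceptible empirical patients number about 5 to 37 of the 96 randomised (96 × 0.05 to 96 × 0.39). Prevalence makes these strata small, and ITT would not change that much.

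**Conclusion.** The point holds for the between-arm comparisons by resistance in final SAP 6.2 and Table 4. They are restricted to a set chosen on events after randomisation, while a comparison that keeps randomisation within strata is available and is not planned.

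The size and direction of any bias cannot be stated from the documents. Under the assumed 95% PP eradication in both arms, a five-point imbalance in exclusions moves the difference by 2.25 to 4.75 points in either direction, and balanced exclusions leave it at 0. The conclusion also assumes that every randomised patient's isolate yields a susceptibility result; the culture criterion makes this likely but does not guarantee it.

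The primary conclusion is not affected, since superiority is tested in both ITT and PP. This is an improvement worth making because it costs almost nothing. It is not a defect in the trial's main result.

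**What to change.** In final SAP 6.2 and Table 4:

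1. Make ITT, with a missing breath test counted as failure, the main set for the between-arm comparisons by resistance. Give risk differences with 95% CIs.
2. Show the PP results beside them as supportive.
3. Report the number excluded from PP, with reasons, by arm and resistance pattern, so that readers can see whether the two sets part and why.
4. Leave the within-therapy susceptible v resistant comparison in PP if preferred, and say that it is not a randomised contrast.
5. In final protocol 10.3, name the analysis set for the susceptibility subgroups so that it agrees with the SAP.

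The cost is one more block in Table 4, a short exclusion table and a few words in 6.2 and 10.3. No new data, visits or patients are needed.
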